8.0 ADVERSE EVENTS

8.1 Definitions

8.1.1 Adverse Event (AE)

An AE is any untoward medical occurrence (e.g., an abnormal laboratory finding, symptom, or disease temporally associated with the use of a drug) in a patient or clinical investigation subject administered a pharmaceutical product and which does not necessarily have a causal relationship with this treatment. An AE can therefore be any unfavorable and unintended sign (including an abnormal laboratory finding), symptom, or disease temporally associated with the use of a medicinal product, whether or not related to the medicinal product.

Laboratory abnormalities that do not require dose modification for entinostat, hospitalization for elective surgery or routine clinical procedures that are not the result of an AE (e.g., surgical insertion of central line) need not be considered AEs and should not be recorded as an AE.

Disease progression should not be recorded as an AE, unless it is attributable by the investigator to the study therapy.

8.1.2 Suspected Adverse Reaction (SAR)

A suspected adverse reaction (SAR) is any AE for which there is a *reasonable possibility* that the drug is the cause. *Reasonable possibility* means that there is evidence to suggest a causal relationship between the drug and the AE. A suspected adverse reaction implies a lesser degree of certainty about causality than adverse reaction, which means any AE caused by a drug.

Causality assessment to a study drug is a medical judgment made in consideration of the following factors: temporal relationship of the AE to study drug exposure, known mechanism of action or side effect profile of study treatment, other recent or concomitant drug exposures, normal clinical course of the disease under investigation, and any other underlying or concurrent medical conditions. Other factors to consider in considering drug as the cause of the AE:

1. Single occurrence of an uncommon event known to be strongly associated with drug exposure (e.g., angioedema, hepatic injury, Stevens-Johnson Syndrome).
2. One or more occurrences of an event not commonly associated with drug exposure, but otherwise uncommon in the population (e.g., tendon rupture); often more than once occurrence from one or multiple studies would be needed before the sponsor could determine that there is *reasonable possibility* that the drug caused the event.
3. An aggregate analysis of specific events observed in a clinical trial that indicates the events occur more frequently in the drug treatment group than in a concurrent or historical control group.

8.1.3 Unexpected AE or SAR

An AE or SAR is considered unexpected if its specificity or severity is not consistent with the applicable product information (e.g., Investigator's Brochure [IB] for an unapproved investigational product or package insert/summary of product characteristics for an approved product). Unexpected also refers to AEs or SARs that are mentioned in the IB as occurring with a class of drugs or as anticipated from the pharmacological properties of the drug, but are not specifically mentioned as occurring with the particular drug under investigation.

8.1.4 Serious AE or SAR

A SAE is one that at any dose (including overdose):

- Results in death
- Is life-threatening¹
- Requires inpatient hospitalization or prolongation of existing hospitalization
- Results in persistent or significant disability or incapacity²
- Is a congenital anomaly or birth defect
- Is an important medical event³
- Pregnancy

¹ "Life-threatening" means that the subject was at immediate risk of death at the time of the SAE; it does not refer to a SAE that hypothetically might have caused death if it were more severe.

² "Persistent or significant disability or incapacity" means that there is a substantial disruption of a person's ability to carry out normal life functions.

³ Medical and scientific judgment should be exercised in deciding whether expedited reporting is appropriate in situations where none of the outcomes listed above occurred. Important medical events that may not be immediately life-threatening or result in death or hospitalization but may jeopardize the patient or may require intervention to prevent one of the other outcomes listed in the definition above should also usually be considered serious. Examples of such events include allergic bronchospasm requiring intensive treatment in an emergency room or at home, blood dyscrasias or convulsions that do not result in inpatient hospitalization, or the development of drug dependency or drug abuse. A new diagnosis of cancer during the course of a treatment should be considered as medically important.

The investigator will report serious, unexpected reactions to the FDA, Syndax, and the IRB in accordance with applicable laws and regulations.

8.2 Documentation of non-serious AEs or SARs

For non-serious AEs or SARs, documentation must begin from day 1 of study treatment and continue until patient completes the 30-day follow-up period assessments.

Collected information should be recorded in the eCRF and source documentation appropriately. Please include a description of the event, its severity or toxicity grade, onset and resolved dates (if applicable), and the relationship to the study drug. Documentation should occur at least monthly.

8.3 SAEs or Serious SARs

8.3.1 Timing

After informed consent but prior to initiation of study medications, only SAEs caused by a protocol-mandated intervention will be collected (e.g. SAEs related to invasive procedures such as biopsies, medication washout).

For any other experience or condition that meets the definition of an SAE or a serious SAR, recording of the event must begin from day 1 of study treatment and continue through the 30-day follow-up period after treatment is discontinued.

8.3.2 Documentation and Notification

SAEs or Serious SARs must be recorded in the SAE console within OnCore[®] for that patient within 24 hours of learning of its occurrence and will reported to SYNDAX.

8.4 Adverse Event Reporting

8.4.1 IRB Reporting Requirements:

UNC:

- The UNC-IRB will be notified of all SAEs that qualify as an Unanticipated Problem as per the UNC IRB Policies using the IRB's web-based reporting system (see section 9.5.3) within 7 days of the Investigator becoming aware of the problem.

Pregnancy

Pregnancies and suspected pregnancies (including a positive pregnancy test regardless of age or disease state) of a female subject occurring while the subject is on study, or within 30 days of the subject's last dose of study should be recorded as SAEs. The patient is to be discontinued immediately from the study.

The female subject should be referred to an obstetrician-gynecologist, preferably one experienced in reproductive toxicity for further evaluation and counseling.

The Investigator will follow the female subject until completion of the pregnancy, and must document the outcome of the pregnancy (either normal or abnormal outcome) and report the condition of the fetus or newborn to the UNC Study Coordinator. If the outcome of the pregnancy was abnormal (e.g., spontaneous or therapeutic abortion), the Investigator should report the abnormal outcome as an AE. If the abnormal outcome meets any of the serious criteria, it must be reported as an SAE.

8.4.2 **Syndax Reporting Requirements:**

The investigator must inform Syndax in writing using a SAE form or MEDWATCH 3500A form of any SAE within 24 hours of being aware of the event. The date of awareness should be noted on the report. The written report must be completed and supplied to Syndax within 24 hours/1 business day at the latest on the following working day. The initial report must be as complete as possible, including details of the current illness and (serious) AE, and an assessment of the causal relationship between the event and the investigational product(s). SAE reports must include the Syndax Study ID Number, the Site Number, the Subject ID Number, and the name of the PI. Information not available at the time of the initial report (e.g., an end date for the AE or laboratory values received after the report) must be documented on a follow-up report. A final report to document resolution of the SAE is required. SAEs should be sent via email to: [contact]

8.4.3 **FDA Expedited Reporting requirements for studies conducted under an IND:**

A sponsor must report any suspected adverse reaction that is both serious and unexpected to the FDA. The sponsor must report an AE as a suspected adverse reaction only if there is evidence to suggest a causal relationship between the drug and the adverse event, such as:

1. A single occurrence of an event that is uncommon and known to be strongly associated with drug exposure (e.g., angioedema, hepatic injury, Stevens-Johnson Syndrome);
2. One or more occurrences of an event that is not commonly associated with drug exposure, but is otherwise uncommon in the population exposed to the drug (e.g. tendon rupture);
3. An aggregate analysis of specific events observed in a clinical trial (such as known consequences of underlying disease or condition under investigation or other events that commonly occur in the study population independent of drug therapy) that indicates those events occur more frequently in the drug treatment group than in a concurrent or historical control group.

The sponsor must submit each IND safety report on FDA Form 3500A. Each notification to FDA must bear prominent identification of its contents, i.e., 'IND Safety Report,' and must be transmitted to the review division that has the responsibility for review of the IND. In each IND

safety report, the sponsor must identify all IND safety reports previously submitted to FDA concerning a similar suspected adverse reaction and must analyze the significance of the suspected adverse reaction in light of previous, similar reports or any other relevant information.

Timing

FDA must be notified of potential serious risks within 15 calendar days after the sponsor determines the event requires reporting. FDA must be notified of unexpected fatal or life-threatening suspected adverse reactions as soon as possible but in no case later than 7 calendar days after the sponsor's initial receipt of the information. If the results of a sponsor's investigation show that an AE not initially determined to be reportable is reportable, the sponsor must report such suspected adverse reaction in an IND safety report as soon as possible, but in no case later than 15 calendar days after the determination is made.

Follow-up

The sponsor must promptly investigate all safety information it receives. Relevant follow-up information to an IND safety report must be submitted as soon as the information is available and must be identified as such, i.e., 'Follow-up IND Safety Report.' Additionally, upon request from FDA, the sponsor must submit to FDA any additional data or information that the agency deems necessary, as soon as possible, but in no case later than 15 calendar days after receiving the request.

Notification of Investigators

The sponsor must notify all participating investigators (i.e., all investigators to whom the sponsor is providing drug under its INDs or under any investigator's IND) in an IND safety report of potential serious risks, from clinical trials or any other source, as soon as possible, but in no case later than 15 calendar days after the sponsor determines that the information qualifies for reporting.

Process

If the sponsor deems that an event is both a serious adverse reaction (SAR) AND unexpected, it must also (in addition to OnCore[®]) be recorded on the MedWatch Form 3500A as per 21 CFR 312.32. Unexpected AEs or adverse reaction refers to an event or reaction that is not listed in the investigator's brochure or is not listed at the specificity or severity that has been observed; or if an investigator's brochure is not required or available, is not consistent with the risk information described in the general investigation plan or elsewhere in the current IND application.

The MedWatch form should be submitted on MedWatch by the study coordinator.

The MedWatch 3500a form can be accessed at:

<http://www.fda.gov/Safety/MedWatch/HowToReport/DownloadForms/default.htm>.

Note: (Please be sure and access form 3500a, and not form 3500).

The MedWatch form should also be sent to the UNC-CH Regulatory Associate and the IND Specialist within 48 hours of the sponsor being aware of the event. The Regulatory Associate

with the aid of the IND Specialist will submit the IND Safety Report via IND serial submission to the FDA review division.

All IND safety reports must be submitted on Form 3500A and be accompanied by Form 1571. The FDA must be notified of any unexpected or life-threatening suspected adverse reactions as soon as possible, but no later than 7 calendar days of learning of the event.

Additional Reporting Requirements

The following additional items must be reported via IND safety report:

1. *Findings from other studies.* The sponsor must report any findings from epidemiological studies, pooled analysis of multiple studies, or clinical studies, whether or not conducted under an IND, and whether or not conducted by the sponsor, that suggest a significant risk to humans exposed to the drug.
2. *Findings from animal or in vitro testing.* The sponsor must report any findings from animal or *in vitro* testing, whether or not conducted by the sponsor, that suggest a significant risk in humans exposed to the drug, such as reports of mutagenicity, teratogenicity, or carcinogenicity, or reports of significant organ toxicity at or near the expected human exposure.
3. *Increased rate of occurrence of serious suspected adverse reactions.*

Additional Guidance

Please refer to 21CFR312.32 and “Guidance for Industry and Investigators: Safety Reporting Requirements for INDs and BA/BE Studies” for additional information and reporting requirements. All IND Safety Reports will be submitted in accordance with regulations and guidance provided.

8.5 Data and Safety Monitoring Plan

The Principal Investigator will provide continuous monitoring of patient safety in this trial with periodic reporting to the Data and Safety Monitoring Committee (DSMC).

Meetings/teleconferences will be held at a frequency dependent on study accrual and in consultation with the study Biostatistician. These meetings will include the investigators as well as protocol nurses, clinical research associates, regulatory associates, data managers, biostatisticians, and any other relevant personnel the principal investigators may deem appropriate. At these meetings, the research team will discuss all issues relevant to study progress, including enrollment, safety, regulatory, data collection, etc.

The team will produce summaries or minutes of these meetings. These summaries will be available for inspection when requested by any of the regulatory bodies charged with the safety of human subjects and the integrity of data including, but not limited to, the oversight (Office of Human Research Ethics (OHRE) Biomedical IRB, the Oncology Protocol Review Committee (PRC) or the North Carolina TraCS Institute Data and Safety Monitoring Board (DSMB).

The UNC-CH LCCC Data and Safety Monitoring Committee (DSMC) will review the study on a regular (quarterly to annually) basis, with the frequency of review based on risk and complexity as determined by the UNC-CH Protocol Review Committee. The UNC PI will be responsible for submitting the following information for review: 1) safety and accrual data including the number of patients treated; 2) significant developments reported in the literature that may affect the safety of participants or the ethics of the study; 3) preliminary response data; and 4) summaries of team meetings that have occurred since the last report. Findings of the DSMC review will be disseminated by memo to the UNC PI, PRC, and the UNC IRB and DSMB.

9.0 STATISTICAL CONSIDERATIONS

This is a phase II study using one FDA-approved drug, pembrolizumab, and an investigational agent, entinostat.

9.1 Study Design/Study Endpoints

All patients will receive pembrolizumab plus entinostat for up to 27 weeks. Drugs will be sequentially introduced; such that correlative analysis can be performed to investigate the indirect immunomodulatory effect of entinostat alone and in combination with pembrolizumab by performing serial peripheral blood collections (4 time points) and tumor collection (2 time points). Assessment of response to the treatment combination will be assessed at week 10 and then every 6 weeks of pembrolizumab treatment for up to 27-weeks.

9.1.1 Definitions

Evaluable patients are those who complete all activities by at least day 22, namely: (a) they have received at least one and up to 4 entinostat weekly doses on day 1 and day 8, 15 and 22 (b) they have received the first pembrolizumab infusion on day 22 (± 2 days), and (c) they have completed day 22 (± 2 days) mandatory tumor biopsy. The rationale for this is to answer the primary translational endpoint regarding entinostat-alone immunomodulatory effects in peripheral blood and tumor tissue with sufficient power.

- SAE are events that meet FDA's definition as defined in [section 8.1.4](#) of the protocol irrespective of attribution to study drug(s). Subjects who receive at least one dose of entinostat are evaluable for safety.

- ORR by RECIST 1.1 criteria is the sum of complete response and partial response.

- PFS is measured from the date of enrollment on study to the date of documented progression. The rate of patients who are progression-free will be specifically calculated at 27-weeks (approximately 6 months) from study entry.

- OS is measured from the date of enrollment on study to the recorded date of death. The rate of patients who are alive at 27-week (approximately 6 months) will be specifically calculated for the study.

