2.0 STUDY OBJECTIVES

2.1 Primary Objective

Assess the incidence of conversion of non-inflamed (TIL/TAL-absent by histopathologic analysis of H&E-stained tissue section from archived metastatic melanoma tumors) to inflamed melanomas following 3 weeks of entinostat monotherapy by performing histopathologic analysis of representative H&E-stained tissue sections from melanoma tumors before treatment and in the end of cycle 1, beginning of cycle 2 (day 22±2 days), immediately before concurrent pembrolizumab-entinostat treatment on day 22 (±2 days) following single-agent entinostat treatment.

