7.4.2 Study Day 22 ± 2 days (D1 of Cycle 2/Week 4)

1. Clinical evaluation: focused history and physical exam,
2. ECOG performance status,
3. 12-lead ECG,
4. Laboratory studies:
 - Hematology
 - Serum Chemistries
 - Collect peripheral blood for isolation of PBMCs (approximately 50 mL)
5. Mandatory Fresh Tumor biopsy (excisional, punch, or CT-guided),
6. Concomitant medication review,
7. Toxicity Assessment,
8. Patient pill diary check,
9. Entinostat administration: 5mg PO to be administered after mandatory biopsy; also dispense two 5-mg pills for administration on D28 and D35,
10. Pembrolizumab administration: 200 mg IV dose; to be administered after mandatory biopsy and after entinostat intake.

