9.2 Sample Size, Accrual and Duration of Accrual

Our goal is to enroll at least 10 evaluable patients. The immune-mediated mechanism of action of entinostat alone (primary translational endpoint) will be evaluated on representative H&E-stained tissue sections from tumor tissues collected at baseline and on day 22 by standard pathology analysis. This analysis will be conducted by [name], study pathologist. Density of TIL/TALs in these H&E-stained sections will be scored as a 0, 1+ (non-brisk), 2+ (brisk) ordinal variable¹⁵¹. By definition, upon enrollment if TILs are present based on H&E stained sections, they must be $\leq 1\%$ of the total number of cells in the specimen. A non-inflamed melanoma may have been ‘successfully’ converted to an inflamed melanoma following 21 days of entinostat ‘priming’ if the histopathologic analysis of day 22 melanoma biopsies shows any (i.e. brisk or non-brisk) evidence of TIL/TAL. In other words, we will capture the incidence of conversion as a dichotomous variable, present (i.e. brisk or non-brisk) or absent. Twenty-one days of entinostat ‘priming’ would be considered to have an immunomodulatory effect if at least 3 out of 10 evaluable patients show conversion of their melanomas from ‘non-inflamed’ to ‘inflamed’. This test has a type I error rate of 0.04 if the true rate is 0.08 and power of 83% if the true rate is 0.4.

The secondary endpoint is antitumor response by RECIST 1.1. Given that one of the determinants of response to single-agent PD-1 inhibitors is pre-existing TIL/TAL²⁹, we postulate that patients with metastatic melanoma and zero TIL/TAL will have nearly zero response rate. With 10 patients the exact 95% confidence interval for response rate is (0, 0.31) if 0 responses are observed out of 10 patients, and (0, 0.45) if 1 response is observed out of 10 patients.

Assuming that 20% of patients will not be evaluable due to screen failure, toxicity or rapid disease progression, and another 30% of enrolled patients will not have interpretable tumor biopsies on day 22 due to necrosis, stromal contamination or overall low quality, the total number of enrolled patients should be set to 14.

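### The evaluable set for the entinostat-alone primary endpoint requires a pembrolizumab infusion given after the endpoint biopsy, and counts a post-biopsy entinostat dose as exposure

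*Combined protocol and SAP*

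**What the plan says.** Section 9.1.1 defines a single evaluable set with three conditions:

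- (a) entinostat exposure: "they have received at least one and up to 4 entinostat weekly doses on day 1 and day 8, 15 and 22";
- (b) pembrolizumab: "they have received the first pembrolizumab infusion on day 22", with a window of ±2 days;
- (c) the day-22 (±2 days) biopsy has been completed.

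The purpose given for this set is the "primary translational endpoint regarding entinostat-alone immunomodulatory effects in peripheral blood and tumor tissue with sufficient power". Section 9.2 then uses it as the denominator of the primary decision rule: at least 3 conversions among 10 evaluable patients.

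Section 7.4.2 fixes the order of events on day 22. Entinostat is "5mg PO to be administered after mandatory biopsy". Pembrolizumab is a "200 mg IV dose; to be administered after mandatory biopsy and after entinostat intake".

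The primary objective in section 2.1 is conversion "to inflamed melanomas following 3 weeks of entinostat monotherapy", which section 1.1 sets out as doses on days 1, 8 and 15.

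Section 5.1(b) takes a different line on early toxicity. A patient who develops toxicity from either drug, but whose blood, tissue and tumor assessments are done by at least week 3, has completed all trial requirements.

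**The concern.** Whether a patient enters the denominator should depend on what happened up to the endpoint biopsy. Condition (b) makes it depend on something that happens afterwards. The infusion may be withheld or delayed for toxicity or progression, which section 9.2 itself names among the reasons patients will not be evaluable. Those reasons may be related to whether the tumor converted. Dropping such a patient discards a complete primary observation and may select on the outcome, in a trial that plans for about 10 observations.

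Condition (a) has a related fault. The day-22 dose comes after the biopsy and cannot contribute to priming, yet it is counted as exposure. The floor of one dose is also well short of the three weeks of monotherapy in the objective.

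**Working it through.** **Stated figures.** Section 9.2 gives n = 10, success at 3 or more conversions, null rate 0.08 with type I error 0.04, and alternative rate 0.4 with power 83%. With X binomial, P(X ≥ 3) = 1 − P(0) − P(1) − P(2):

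- at 0.08: 1 − 0.4344 − 0.3777 − 0.1478 = 0.0401;
- at 0.40: 1 − 0.0060 − 0.0403 − 0.1209 = 0.8327 (from unrounded terms).

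Both agree with the plan.

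**Order of events.** Section 7.4.2 gives biopsy, then entinostat, then pembrolizumab. Neither day-22 drug can alter the tissue scored, but 9.1.1 requires one and counts the other.

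**Size.** The documents do not say how many patients would be affected, so the counts below are assumptions.

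1. *Scorable patients dropped and not replaced, cut-off still 3.* At 0.40, n = 9 gives 1 − 0.0101 − 0.0605 − 0.1612 = 0.768. With n = 8, power is 0.685.

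2. *Dropped patients replaced, so that 10 are still analysed.* Nominal power is kept and the risk becomes selection. The upper bound on false positives arises when all m dropped patients are non-converters: every conversion among the 10 + m biopsied then stays in the analysed set, and the chance of success at 0.08 is P(X ≥ 3) with n = 10 + m.
   - m = 1: 1 − 0.3996 − 0.3823 − 0.1662 = 0.052
   - m = 2: 0.065
   - against 0.040 with no selection.

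   If the dropped patients were converters, the bias would run the other way. The documents do not indicate a direction.

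3. *Partly primed patients.* Assume an under-exposed patient converts at 0.24, the midpoint of 0.08 and 0.40. With one such patient in 10, power is P(A ≥ 3) + P(A = 2) × 0.24 for A binomial (9, 0.40): 0.7682 + 0.1612 × 0.24 = 0.807. With two, it is 0.778.

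**Consequence for the cut-off.** If removing condition (b) raises the number analysed, the rule needs a cut-off for each n:

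| Rule | Type I error at 0.08 | Power at 0.40 |
|---|---|---|
| 3 of 10 | 0.040 | 0.833 |
| 3 of 11 | 0.052 | 0.881 |
| 4 of 11 | 0.009 | 0.704 |
| 3 of 12 | 0.065 | 0.917 |
| 4 of 12 | 0.012 | 0.775 |

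The synopsis allows 10 to 12 evaluable patients, so the rows for 11 and 12 lie within the planned range.

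**The case against.** The infusion follows the biopsy at the same visit, so few patients may be biopsied and then miss the window. Section 9.2 aims for at least 10 evaluable patients and allows for losses; if a dropped patient is replaced, the cost is enrolment rather than power. A single set also serves the combination endpoints, for which receipt of pembrolizumab is a sensible condition. Section 5.1(b) concerns completion of the trial, not evaluability. All of this stands and limits the size of the problem. It does not justify condition (b) for an endpoint that 9.1.1 itself describes as entinostat alone.

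Three stronger readings are tempting but not supported.

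- *Wholly unprimed patients could enter the set.* Read literally, condition (a) would admit someone whose only dose was on day 22. But section 5.2 starts entinostat on study day 1, section 7.4.1 has that dose taken in front of staff, and (a) can itself be read as requiring day 1. Such a patient should hardly occur. Power figures of 0.781 or 0.717, for one or two patients converting at 0.08, describe that case and should not be used. The realistic defect is under-priming.
- *Unreadable biopsies count as failures.* Condition (c) asks only that the biopsy be completed, so a reader might apply a rate of 0.4 × 0.7 = 0.28 and obtain power of 0.56. Section 9.2 points the other way: it says "another 30% of enrolled patients will not have interpretable tumor biopsies on day 22" and treats these as losses when setting enrolment. What remains is that 9.1.1 does not repeat the requirement.
- *The stated type I error and power are wrong.* They reproduce exactly to the precision printed.

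**Conclusion.** The definition is wrong as written for the primary endpoint. It conditions an entinostat-alone analysis on a post-biopsy infusion, so scorable biopsies can be lost for reasons that may relate to outcome, and this is at odds with 5.1(b). It also counts a post-biopsy dose as exposure and lets patients with as little as one of three priming doses into an analysis of three weeks' monotherapy.

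The size cannot be fixed from the documents. The 0.77 assumes one loss without replacement. The 0.052 and 0.065 are upper bounds that assume replacement and that the one or two dropped patients were all non-converters. Confidence is high for condition (b). The point on condition (a) is real but smaller, and its power illustration rests on the assumed rate of 0.24.

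**What to change.** For the primary endpoint, in section 9.1.1:

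1. Delete condition (b) and keep it only for endpoints on response to the combination.
2. Count only entinostat doses taken before the biopsy, and state the minimum number required, with a reason tied to the three-week objective. Dropping the day-22 dose from the count would not by itself remove patients with a single priming dose.
3. State, in line with 9.2, that the day-22 biopsy must be interpretable. This too selects on a post-baseline feature, but an unreadable core has no outcome to score; fix the criteria in advance and report how many patients are excluded.
4. Reconcile the definition with section 5.1(b).
5. State the cut-off for each possible number evaluable, since leaving it at 3 takes type I error to 0.052 with 11 patients and 0.065 with 12.

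A sensitivity analysis in patients who took all three pre-biopsy doses is optional; with about 10 patients it would be descriptive.

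The cost is small but not nil. Section 9 is part of the protocol, so the change is an amendment that needs IRB approval before use (section 10.6). No treatment, visit or sample changes.
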